7.4.5 Handling AE

All AEs which occur during the study period must be recorded in detail in the Case Report Form, including symptoms and signs, start date/end date, duration, severity, treatment and results, and causality with the investigational product even if they are not related to the investigational product. In addition, if possible, the AE shall be observed until it is recovered to pre-administration or baseline level, or until the investigator can determine that the AE has been normalized, or until further observation is deemed unnecessary.

Handling of the AE is categorized as follows:

- 1) Drug administration maintained
- 2) Drug administration interrupted
- 3) Drug administration permanently discontinued

- 4) N/A: The subject has deceased, or administration is terminated when the AE occurs
- 5) Unknown

Treatments of the AE are categorized as follows:

- 1) Perform drug treatment of the AE
- 2) Perform non-drug treatment of the AE
- 3) Perform drug/non-drug treatment of the AE
- 4) No drug/non-drug treatment of the AE

Results of the AE are categorized as follows:

- 1) Recovered (resolved)
- 2) Recovering (being resolved)
- 3) Not recovered (not resolved)
- 4) Recovered (resolved) with sequelae
- 5) Death possibly related to the AE
- 6) Death not related to the AE
- 7) Unknown

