#### 3.1.3 Previous/Concomitant Medications (Treatment)

All medications and treatments administered within 6 months before Visit 1 (screening) were surveyed. Previous medications and previous treatments shall be defined as all previously collected medications and treatments before Visit 2\*. Concomitant medications and treatments\*\* shall refer to all medications that have been administered at least once starting from Visit 2 and throughout the clinical study. The categories of collected medications and treatments shall follow this definition. The following were also surveyed for each medication:

- \*Prior medications and prior treatments: Start date ≤ Visit 2 (Day 0)
- \*\*Concomitant medications and concomitant treatments: End date  $\geq$  Visit 2 (Day 0) or if ongoing
- Brand name
- Indications for medication administration (reason for administration)
- Dose/strength, administration route, number of administrations
- Start and discontinuation dates of administration (whether to continue when the clinical study is terminated)

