#### 4.9 Analysis of Other Groups

When conducting adverse event and efficacy assessments, subgroup analysis shall be performed by considering the items shown below.

If necessary, tests shall be performed on the differences between groups, and in the case of continuous data, analysis shall be performed using a two sample t-test (Wilcoxon's signed rank test if Shapiro-Wilk test results do not satisfy the assumption of normal distribution), while the Pearson's Chi-square test (Fisher's exact test if cells with expected frequency < 5 exceeds 20%) shall be used for categorical data.

- Sex (male, female)
- Age (≤ median, > median)
- Baseline BMI (≤ median, > median)
- Presence or absence of medical history
- Presence or absence of concomitant drugs
- Disease severity (CMTNS-v2) (mild, moderate)

If the subjects within each subgroup are  $\leq$  30%, analysis shall not be performed. For example, if  $\leq$  30% of the total number of subjects is male, no subgroup analysis for sex shall be performed, and whether an analysis should be performed shall be determined in a data review meeting prior to datalock.

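### The concomitant-drug subgroup counts drugs started after dosing, including drugs given for adverse events, so its adverse event comparison is biased by construction and its efficacy comparison is not a baseline subgroup

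*SAP*

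**What the plan says.** - **The factor.** SAP 4.9 (and 2.3) lists "Presence or absence of concomitant drugs" among six subgroup factors. Protocol 8.1.4 and the synopsis list the same factor. None ties it to baseline, although BMI in the same lists is specified as a baseline value.
- **Where it is used.** SAP 4.9: "When conducting adverse event and efficacy assessments, subgroup analysis shall be performed by considering the items shown below". Formal comparison is conditional: "If necessary, tests shall be performed on the differences between groups".
- **The definition.** In SAP 3.1.3 concomitant medications "shall refer to all medications that have been administered at least once starting from Visit 2 and throughout the clinical study". The date rule is an end date on or after "Visit 2 (Day 0) or if ongoing". SAP 3.1.3 makes this binding: "The categories of collected medications and treatments shall follow this definition". Footnote 12 to the protocol's schedule of visits (6.1) defines the term in the same way.
- **What is recorded.** SAP 3.1.3 collects start and stop dates and "Indications for medication administration (reason for administration)", but the subgroup definition uses neither the start date nor the reason.
- **Drugs for AEs.** Protocol 7.4.5 has "Perform drug treatment of the AE" as one of its AE treatment categories. SAP 4.7 analyses treatment-emergent AEs (TEAEs), which fall in the same post-dose window as the concomitant drugs.
- **A conflicting description.** Protocol 8.4.2 gives concomitant medications as an example of a pre-treatment characteristic.

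**The concern.** A subgroup factor should be fixed before the outcome can influence it. Here the outcome helps to set the factor. Someone who takes no drug at Day 0, has a TEAE and receives a drug for it moves from the absence group to the presence group because of the event. The absence group is left with subjects who had no TEAE or only TEAEs not treated with a drug.

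The table would then show more AEs with concomitant drugs even if those drugs have no effect on AE risk. Safety is the primary objective, so a reader could take this as a safety signal for combined use, or take the absence group as evidence of unusually good tolerability. For efficacy the factor is also settled after dosing, so a difference between the groups does not describe patients who could be identified at the start of treatment.

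**Working it through.** The documents state no figure on this point, so there is none to reproduce. The size is illustrated under assumptions.

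**From the documents:** N = 12, single arm; a subgroup holding 30% or less of subjects is not analysed. Since 0.30 × 12 = 3.6, each group needs at least 4 subjects, so the presence group must have 4 to 8.

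**Assumed:** b = chance of taking a drug for a reason other than an AE; a = chance of a TEAE, the same for everyone and independent of b; t = chance that a TEAE is treated with a drug. The true difference in AE risk is therefore zero.

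**Formulas**
- Share in the presence group: s = b + (1 − b)·a·t
- AE rate, presence: [b·a + (1 − b)·a·t] / s
- AE rate, absence: (1 − b)·a·(1 − t) / (1 − s)
- Chance that the subgroup is kept: P(4 ≤ X ≤ 8), X ~ Binomial(12, s)

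**Example, b = 0.4, a = 0.5, t = 0.6**
- s = 0.4 + 0.6 × 0.5 × 0.6 = 0.58
- Presence: (0.20 + 0.18) / 0.58 = 65.5%
- Absence: 0.6 × 0.5 × 0.4 / 0.42 = 0.12 / 0.42 = 28.6%
- Gap: 37 points, all of it artefact

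| t (b = 0.4, a = 0.5) | s | AE, presence | AE, absence | False gap | Chance kept |
|---|---|---|---|---|---|
| 0.3 | 0.49 | 59% | 41% | 18 points | 85% |
| 0.6 | 0.58 | 66% | 29% | 37 points | 79% |
| 0.9 | 0.67 | 70% | 9% | 61 points | 59% |

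**Wider inputs.** With b from 0.2 to 0.6 and a from 0.3 to 0.7, the gap is 9 to 24 points at t = 0.25, 19 to 42 at t = 0.5, and 42 to 92 at t = 1. At t = 1 the absence group has no AEs by definition. A gap below 9 points is possible: a = 0.9, b = 0.4, t = 0.3 gives about 7.

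**Chance of being kept, other inputs (a = 0.5, t = 0.6).** 82% at b = 0.2, 44% at b = 0.6, 23% at b = 0.7 and 8% at b = 0.8.

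**If a test is run.** At most two cells of a 2 × 2 table of 12 subjects can have an expected count of 5 or more, so SAP 4.9 always leads to Fisher's exact test. By exact enumeration at b = 0.4 and a = 0.5, among runs that pass the size rule, it rejects at 0.05 in 1.3% at t = 0, 6.6% at t = 0.5 and 47% at t = 1.

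**Efficacy.** Let D be the difference in mean change score between subjects with and without a TEAE. If drug starts are otherwise unrelated to outcome, the subgroup difference is D times the AE gap: 0.37·D in the example, and zero if D = 0. The documents give neither the size nor the sign of D.

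**With a baseline definition.** If drug use at Day 0 is unrelated to AE risk, the expected gap is zero for every a and b. Fisher's test then rejects in 1.0% to 1.3% of runs over the same values of a and b.

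**The case against.** The case for leaving this alone is that little depends on it. It is one of six factors in a 12-subject single-arm phase 1/2a study whose data are to be reviewed descriptively. Tests are run only if judged necessary, a data review meeting before datalock decides whether to run the analysis, and the main TEAE summary in SAP 4.7 does not use the subgroup. Protocol 8.4.2 also suggests that a baseline factor was intended.

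Most of that stands, and it limits the weight of the point. It does not answer it. The bias lies in the descriptive incidences, with or without a p-value. The size rule screens for small groups, not for how they were formed. The meeting is asked whether to run the analysis, not to redefine the factor. Protocol 8.4.2 shows a likely intent, but the binding definition in SAP 3.1.3 says otherwise.

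Two stronger readings are not supported. A reader might infer that the efficacy comparison is also biased by construction. It is not: the efficacy outcome does not place anyone in a group, so bias there needs AEs or drug starts to be linked to outcome. A reader might also infer that the subgroup will usually survive the 30% rule, or will usually be dropped. The documents give no drug-use or AE rates, and the chance of being kept ran from 8% to 85% over the inputs in the table and the list of other inputs above.

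**Conclusion.** The point holds for AEs by the SAP's own definition. If drug use for other reasons is unrelated to AE risk, any drug-treated TEAE in a subject taking no other drug tilts the comparison towards more AEs in the presence group. The 18 to 61 point range rests on assumed values (40% unrelated use, 50% AE risk, 30% to 90% of AEs drug-treated) and is an illustration, not a forecast.

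For efficacy the conclusion is narrower. The split is post-baseline and is not interpretable as a baseline subgroup effect; the existence and direction of any bias are unknown.

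The overall safety results are unaffected. This is a modest defect in an exploratory table, worth correcting because the correction is cheap.

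**What to change.** - **Redefine the factor** in SAP 2.3 and 4.9, and in protocol 8.1.4 and the synopsis so that the documents agree: a subject is in the presence group if at least one drug was started before the first administration and was ongoing at Day 0. Drugs started after the first dose, and drugs recorded as AE treatment, do not count. This also agrees with protocol 8.4.2.
- **State how Day 0 and partial start dates are classified.** SAP 3.1.3 counts a Day 0 start as prior medication, and SAP 4.3 Table 1 sets some partial start dates to Day 0. A strict before-Day-0 rule could drop true baseline drugs with a partial date; an on-or-before rule could admit drugs started after dosing. The recorded reason for administration could decide such cases.
- **Report post-dose drug use descriptively**, by listing, without comparing AE or efficacy results between users and non-users.

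The cost is a few sentences in two documents, agreed before datalock. No new data are needed: start and stop dates and the reason for each drug are already collected.
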